7.4 Efficacy and pharmacodynamic measurements

Objective	Variables
To evaluate the effect of two different doses of AZD9773 versus placebo on ventilator-free days over 28 days and further characterise the safety profile of AZD9773.	TNF α , IL-6, IL-8 Multiplex cytokine assay for exploratory chemokines Neutralising antibody assay Procalcitonin Lactate VFDs 7-day mortality 28-day mortality Mortality at Day 90 Organ failure-free days Shock-free days ICU-free days

7.4.1 Efficacy

Mortality will be assessed at the timepoints specified in [Table 1](#). VFDs, organ failure-free days, shock-free days and ICU-free days will be assessed at the timepoints specified in [Table 1](#). For further details of these parameters, see Section [7.6](#).

7.4.2 Cytokine serum concentrations

Blood samples for measurement of cytokine serum concentrations will be collected from all patients at the timepoints specified in [Table 1](#) by the investigator or medically qualified personnel, according to methods specified by Covance. Details on sampling and handling procedures will be specified in the study laboratory manual.

Cytokine samples will be taken as follows:

- TNF α for enzyme-linked immunosorbent assay (ELISA) analysis will be taken at screening - pre-infusion; Day 1 at 1-2 hours after the end of infusion; before the morning dose on Day 2, 1-2 hours after the end of infusion on Day 2, before the morning dose on Days 4 and 6; and on Days 7, 10 and 15.
- IL-6, and IL-8 samples for ELISA analysis will be taken at screening - pre-infusion; Day 1 at 1-2 hours after the end of infusion, and before the morning dose on Days 2, 4, and 6.
- Multiplex assay samples for exploratory chemokines will be taken at screening - pre-infusion; Day 1 at 1-2 hours after the end of infusion; before the morning dose on Day 2, 1-2 hours after the end of infusion on Day 2, before the morning dose on Days 4 and 6; and on Days 7, 10 and 15. Samples will be used to evaluate the potential utility of a multiplex chemokine assay.

7.4.3 Neutralising antibody assay

Blood samples for neutralising antibody (NAB) assay will be collected according to standard procedures at timepoints specified in [Table 1](#) by the investigator or medically qualified personnel, according to methods specified by Covance or AstraZeneca. In addition, samples may be used for the improvement or further development of assay methodology. Details on sampling and handling procedures will be specified in the study laboratory manual. Blood samples may be taken from a peripheral or central venous source or from an arterial source. The time that each blood is taken will be recorded in the eCRF. If a sample is missed, the next sample should be taken as scheduled.

The NAB assay will be analysed by Covance Laboratories Ltd., [name]. Samples will be labelled, stored and shipped according to AstraZeneca Standard Operating Procedures.

7.4.4 Lactate and procalcitonin

Blood samples for analysis of serum lactate and serum procalcitonin will be collected according to local standard procedures at the timepoints scheduled in [Table 1](#) by the investigator or medically qualified personnel. However, for serum lactate, there must be an interval of at least 6 hours between the screening samples and the samples at Day 1. To preserve this minimum 6-hour window, the Day 1 samples may in fact need to be taken on Day 2.

Blood samples for lactate assessments will be analysed locally. Each laboratory will be required to provide up-to-date reference ranges. See [Section 8.1](#) for the total estimated volume of blood samples to be collected.

7.4.5 Patient reported outcomes (PRO)

7.4.5.1 Short Form 36 Health Survey, version 2 Acute

Assessment of patients' HRQoL will be derived from the Short Form 36 Health Survey, version 2 Acute (SF-36v2 Acute) questionnaire. The SF-36v2 Acute is a multi-purpose, short-form health survey with only 36 questions, which is provided in [Appendix K](#). It yields an 8-scale profile of HRQoL scores (Physical functioning Role-physical, Bodily pain, General health, Vitality, Social functioning, Role-emotional, Mental health) as well as a psychometrically based physical (physical component score) and mental health summary (mental component score) measures and a preference based health utility index.

The SF-36v2 Acute differs from the standard SF-36 in that the recall period for 6 of the 8 scales (Role-physical, Bodily pain, Vitality, Social functioning, Role-emotional and Mental health) changes from "the past 4 weeks" to "the past week". Two scales, Physical functioning and General health do not have a recall period; the items and instructions for these scales are identical across acute and standard forms. This version was chosen for the study as the 1-week recall period seems more appropriate for these scales specifically at Day 29.

Additionally for this study, 1 further change will be made to the SF-36v2 Acute. The original question 2 from the standard version – "Compared to 1 year ago, how would you rate your health in general now?" will replace the question 2 from the acute version – "Compared to 1 week ago, how would you rate your health in general now?". This has been included to allow a better understanding of a patient's return to their pre-sepsis levels of HRQoL. As this question does not form a part of any of the main outcome measures outlined above, this does not affect the validity of these endpoints.

The SF-36v2 Acute will be completed at Day 29+2 and at Day 90+14. The Day 29 value will be the initial measurement and the Day 90 value will be taken as follow-up. The SF-36v2 Acute has been validated for multiple completion methods (face-to-face, telephone, IVRS), and the most appropriate method for the patient will be used in this study, although all assessments will be interviewer-led.

7.4.5.2 Administration of PRO questionnaires

The SF-36v2 Acute will be administered at Day 29+2 and at Day 90+14 follow-up contact as outlined in [Figure 1](#) and [Table 1](#).

7.5 Charlson Comorbidity Scale Assessment

Comorbidity at Screening will be assessed using the Charlson Comorbidity Scale (see [Appendix L](#)). Charlson et al ([Charlson et al 1987](#)) developed a score for evaluating prognosis based on age and comorbid conditions. With each increased level of the comorbidity index the cumulative mortality attributable to comorbid disease increases in a step-wise fashion.

7.6 General assessment of sepsis care

7.6.1 Acute Physiology and Chronic Health Evaluation (APACHE) II Scores

APACHE II is a point score based upon 12 routine physiological measurements, age and previous health status that provides a general measure of severity of disease. The measurements needed to calculate APACHE II Scores will be recorded at the timepoints scheduled in [Appendix E](#). APACHE II Scores will be calculated using the assessments from the 24 hours preceding randomisation, not the calendar day.

The 12 physiological measurements should be assessed using standard procedures. These are: temperature (°C), mean arterial pressure (mmHg), heart rate (ventricular response), RR (ventilated or non-ventilated), alveolar to arterial oxygen tension difference (if $\text{FiO}_2 \geq 0.5$) or PaO_2 (if $\text{FiO}_2 < 0.5$), arterial pH (serum bicarbonate if no arterial blood gas for pH [venous mmol/L]), serum sodium (mmol/L), serum potassium (mmol/L), serum creatinine (mg/dL), haematocrit (%), WBC count ($10^3/\text{mm}^3$), and Glasgow Coma Score.

If more than one set of results for any parameter is obtained on the scheduled assessment day, the most out-of-range result will be used for the calculation of the score (eg, the worst results from that day).

For further details of the APACHE II Score, see [Appendix E](#).

7.6.2 Glasgow Coma Score

The assessments needed to calculate the Glasgow Coma Score at screening, Day 6 and Day 15 will be performed as part of the APACHE II assessment at screening and at the timepoints shown in [Appendix F](#) to assess level of consciousness and degree of dysfunction. Patients will be assessed with regard to their level of eye, verbal and motor responses as described in [Appendix F](#). If it is possible to do so, the score should be obtained prior to administering medications that could alter the Glasgow Coma Score. For subsequent daily assessments, the Glasgow Coma Score should be obtained during sedation holiday periods. If this is not possible, the patient's most likely response should be recorded.

7.6.3 Modified Sequential Organ Failure Assessment (SOFA) Scores

A modified SOFA score (ie, not including Glasgow Coma Score) will be calculated at each of the timepoints shown in [Table 1](#). For each of the following routine assessments, the worst value of the day will be recorded in the eCRF: $\text{PaO}_2/\text{FiO}_2$ (mmHg) or oxygen saturation by pulse oximetry ($\text{SpO}_2/\text{FiO}_2$) (mmHg), platelet count, bilirubin, vasopressor use ($\mu\text{g}/\text{kg}/\text{min}$, mmHg), and creatinine ([or urine output]). For laboratory values, use last available (if within 48 hours). On days when laboratory results are unavailable, values will be extrapolated from the previous available values. On days when laboratory results are unavailable, values will be extrapolated from the previous available values ([Section 13.3.5](#)).

The SOFA score for the cardiovascular component does not account for the use of phenylephrine or vasopressin as vasopressor medications. A cardiovascular component score of 3 will be assigned for phenylephrine doses of $\leq 300 \mu\text{g}/\text{kg}/\text{min}$ or vasopressin doses of

< 0.04 units/min. A cardiovascular component score of 4 will be assigned for phenylephrine doses of > 300 µg/kg/min or vasopressin doses of \geq 0.04 units/min.

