2. INTRODUCTION

2.1 Background

2.1.1 Sepsis

Sepsis is a life-threatening disorder that arises through the body's response to infection. It is a complex clinical syndrome that may occur in any age group, and in response to a multitude of microbial pathogens or inflammatory conditions, from multiple different anatomical sites within the body. According to current understanding, the critical pathophysiological trigger is a disturbance in the equilibrium between the pro-inflammatory and anti-inflammatory responses to infection (Marshall 2003).

Severe sepsis and/or septic shock is an important cause of morbidity and mortality in hospitalised patients despite the establishment of specialised critical care units, the availability of broad-spectrum antimicrobial agents, and advancement in the management of inter-current conditions that put patients at risk for the development of severe sepsis and/or septic shock. Indeed, the incidence of severe sepsis and/or septic shock continues to increase, probably due to the overall aging of the general population, the increasing use of invasive procedures and aggressive cancer chemotherapies, and the increase in antibiotic resistance. Despite medical progress, mortality rates remain unacceptably high, and consequently there is an urgent medical need to develop an efficacious treatment in sepsis.

Current therapy for sepsis includes eradication of the infection (eg, using antibiotics and, where appropriate, surgical intervention), resuscitation and restoration of tissue perfusion, restoration of adequate oxygen delivery, and renal replacement therapy. Drotrecogin alfa (activated) recombinant human (rh) activated protein C (Xigris[®], Eli Lilly and Company) has been approved in the USA and European Union (EU) for the treatment of adult patients with severe sepsis and at a high risk of death.

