12.2.7 Calculation and derivation of organ failure assessment

Failure of an organ system will be recorded the first time any of the criteria specified in the individual components of the modified SOFA score are >1 after the start of study drug up to Day 15 (over 14 days). Organ failure-free days will be designated for those days when the organ system modified SOFA score is ≤ 1 . The worst BP and saturation values of the day should be used, and if a drug holiday or no value is collected, the last assessment performed should be the value for that day.

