13.4 Determination of sample size

The sample size has been based on the primary outcome variable of VFDs over 28 days. The Phase IIb study in 81 patients with D-CytoFab has been used as an estimate of the between-patient SD (11.380). Assuming this SD holds for the current study, then 100 patients per group will provide 90% power to detect an underlying true difference in means between a dose of AZD9773 and placebo of 4.2 days using a 10% one-sided significance level.

Given this is an exploratory Phase II study, a 10% one-sided significance level is considered appropriate as this implies a 1 in 10 chance of a false positive finding which is consistent with the aim in Phase II of identifying a promising therapy.

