2.2 Chronic Health Points

Chronic Health Evaluation

If any answer to the Chronic Health Evaluation is *YES*, then the patient has a positive Chronic Disease History. Assign Chronic Health Points (+5 for non-op or emergency post-op; +2 for elective post-op).

Organ insufficiency or immuno-compromised state must have been evident prior to this hospital admission and conform to the following criteria.

LIVER: Biopsy-proven cirrhosis and documented portal hypertension, or episodes of past upper GI bleeding attributed to portal hypertension, or prior episodes of hepatic failure/encephalopathy/coma. Y N

CARDIOVASCULAR: New York Heart Association Class IV. Y N

RESPIRATORY: Chronic restrictive, obstructive, or vascular disease resulting in severe exercise restriction, (ie, unable to climb stairs or perform household duties); or documented chronic hypoxia, hypercapnia, secondary polycythemia, severe pulmonary hypertension (>40 mm Hg), or respirator dependency. Y N

RENAL: Receiving chronic haemo- or peritoneal dialysis. Y N

IMMUNO-COMPROMISED:

The patient has received therapy that suppresses resistance to infection, eg immuno-suppressive agents, chemotherapy, radiation, long term low dose steroids, 10 mg/day prednisone for >1 month prior to hospitalization) or recent high dose steroids (>15 mg/kg/day of hydrocortisone or >3 mg/kg/day of methylprednisolone for >5 days). Y N

The patient has a disease that is sufficiently advanced to suppress resistance to infection, eg leukemia, lymphoma, AIDS, documented diffuse metastatic cancer. Y N

AIDS: acquired human immuno-deficiency syndrome; GI: gastrointestinal

THIS IS A PRINTED COPY OF AN ELECTRONIC DOCUMENT. PLEASE CHECK ITS VALIDITY BEFORE USE.

Clinical Study Protocol Appendix F

Drug Substance	AZD9773
Study Code	D0620C00003
Appendix Edition Number	1
Appendix Date	[REDACTED]

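### The renal SOFA score has no rule for renal replacement therapy, so some dialysis days count as renal failure-free and blunt a formally analysed secondary endpoint

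*Protocol*

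**What the plan says.** Section 7.6.3 has sites record the worst value of each day for the modified SOFA inputs. For the kidney these are "and creatinine ([or urine output]). For laboratory values, use last available (if within 48 hours"). Appendix G scores creatinine below 1.2 mg/dL as 0, 1.2 to 1.9 as 1, 2.0 to 3.4 as 2, and higher bands as 3 and 4. Urine output below 500 mL/day is an alternative route to 3, and below 200 mL/day to 4.

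Section 12.2.7 turns the score into the endpoint: "Organ failure-free days will be designated for those days when the organ system modified SOFA score is" 1 or less. Organ failure-free days at Day 15 (over 14 days) are among the endpoints for formal analysis (synopsis, 13.1, 13.3.6).

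On treatments that distort a score, section 7.6.3 acts for one organ: "The SOFA score for the cardiovascular component does not account for the use of phenylephrine or vasopressin as vasopressor medications", and it then assigns scores for those drugs. There is no counterpart for the kidney, although section 2.1.1 includes "restoration of adequate oxygen delivery, and renal replacement therapy" in current sepsis therapy. Neither Table 1 nor the treatment records required by section 6.5.2 include dialysis given during the study.

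**The concern.** Dialysis clears creatinine. A score built on creatinine alone can therefore improve because the kidney has been replaced, not because it has recovered. The endpoint then gives credit for the days on which renal failure is most certain.

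This is more than a detail left to the statistical analysis plan. The protocol itself fixes the scoring table and the cut-off, and it schedules no dialysis data to which a later rule could be applied. At stake is the ability of organ failure-free days to show a treatment effect on renal failure, in either direction.

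**Working it through.** **The plan's own figure.** The only sizing figure concerns ventilator-free days (13.4): "100 patients per group will provide 90% power to detect" a difference of "4.2 days using a 10% one-sided significance level", with the D-CytoFab study "used as an estimate of the between-patient SD (11.380"). It reproduces. The standardised difference is 4.2 / (11.380 × √(2/100)) = 2.61; subtracting 1.28 gives 1.33, a power of 0.908. The required n is 97 per group. Nothing below alters this.

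**Scoring from Appendix G, with the 12.2.7 cut-off.** Where both inputs are present I took the worse, which the protocol does not state.

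| Patient | Creatinine (mg/dL) | Urine (mL/day) | Score | Day counted as |
|---|---|---|---|---|
| New dialysis | 1.5 | not entered | 1 | failure-free |
| New dialysis | 1.5 | 800 | 1 | failure-free |
| New dialysis | 1.5 | 100 | 4 | failed |
| Chronic dialysis | 6 | not entered | 4 | failed |
| Chronic dialysis | 2.5 | not entered | 2 | failed |
| Chronic dialysis | 1.6 | not entered | 1 | failure-free |
| Chronic dialysis | 1.6 | 50 | 4 | failed |

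The error needs two things together: a worst creatinine below 2.0 mg/dL, and no urine entry below 500 mL/day.

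**Carry-forward.** Section 7.6.3 limits the last laboratory value to 48 hours but also extrapolates from earlier values, and section 13.3.5 carries the renal value forward with no limit. Table 1 scores the SOFA on Days 8 to 10 but schedules no chemistry then. A creatinine lowered by dialysis can thus be carried onto later days.

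**Level shift within an arm.** All inputs are assumptions. Overstatement per patient = proportion dialysed × dialysis days × proportion of those days scored 1 or less.

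- Low: 0.10 × 6 × 0.30 = 0.18 days.
- High: 0.30 × 6 × 0.60 = 1.08 days.
- Wider assumptions (4 to 10 days, 25% to 75% misclassified): 0.10 × 4 × 0.25 = 0.10, up to 0.30 × 10 × 0.75 = 2.25 days.

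**Effect on a contrast.** Suppose one arm has 10 percentage points more dialysis because it has more kidney injury.

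- Extra truly failed days: 0.10 × 6 = 0.60 per patient.
- Misclassified as free: 0.60 × 0.30 = 0.18, up to 0.60 × 0.60 = 0.36.
- Difference still seen: 0.60 − 0.18 = 0.42, down to 0.60 − 0.36 = 0.24 days, with the worse arm still worse.
- With every dialysis day misclassified, the difference is 0.60 − 0.60 = 0.

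If kidney injury is equal and only dialysis use differs by 10 points, the true difference is nil and the arm that dialyses more gains a spurious 0.18 to 0.36 days.

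**Failure present at baseline.** Section 7.6.5 speaks of organ failure developing after study entry. Section 12.2.7 scores every day and makes no exception for failure already present. The two do not define the same quantity.

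**The case against.** A reader might infer that an arm with more kidney injury and more dialysis would look better. The documents do not support that. On the arithmetic above the difference shrinks, at most to zero; it does not reverse. An outright advantage needs unequal dialysis use at equal injury.

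A reader might also infer that chronic dialysis patients are in renal failure on all 14 days. That is usual, not certain: the gap that makes a newly dialysed patient failure-free applies to them too. Section 5.2 does not exclude them, but the evidence that they are expected is thin. Appendix E lists "Receiving chronic haemo- or peritoneal dialysis" on a standard APACHE II form, which also lists conditions removed by exclusion criteria 14 and 16. Section 7.6.7 mentions chronic dialysis only within a cited definition of healthcare-associated infection.

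Two safeguards are real. The worst value of the day counts, so a creatinine measured before an intermittent session is likely to govern. Recorded oliguria scores 3 or 4. Together they confine the problem mainly to continuous therapy without a low urine entry. The eCRF is not shown and may ask for urine output every day, but the wording of 7.6.3 does not require it.

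It can also be said that the vasopressor rule merely extends a row already scored by drug dose, so the renal row is not inconsistent with it. That is fair. The gap stands without the comparison. Renal safety, finally, is followed separately through laboratory data and adverse events and does not depend on this score.

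**Conclusion.** The point holds as a scoring and data-capture gap. Followed as written, the plan counts some dialysis days as renal failure-free and so attenuates any between-arm difference in renal failure within organ failure-free days.

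The size is unknown because the documents give no dialysis rate. The 0.18 to 1.08 days is a shift in the level of every arm under stated assumptions, not a treatment effect. It also refers to the renal component alone. If the endpoint is built as days free of failure in all organs, it is an upper bound under the same assumptions, since a misclassified renal day matters only when the other organs are also free.

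The consequence is limited to one component of one secondary endpoint and to the SOFA summaries. Ventilator-free days, the sample size and mortality are untouched.

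**What to change.** 1. Add a daily yes/no item for renal replacement therapy to the SOFA page of the eCRF and to Table 1.
2. In 7.6.3, 12.2.7 and Appendix G, score the renal component above 1 (failed) for the endpoint derivation on any day the therapy is given.
3. State that the worse of creatinine and urine output is used when both are available.
4. Reconcile 7.6.5 with 12.2.7 on organ failure already present at study entry.
5. Keep the renal component for patients on chronic dialysis, since dropping it would give them a differently built endpoint. If their number warrants it, show a sensitivity analysis without these patients.

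The cost is one more eCRF item, a line in the derivation and a further small departure from the published SOFA, from which the protocol already departs. The item must be in place while data are being collected. Nothing here changes patient care.

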septic process and not be explained by a chronic condition or by effects of concomitant therapy. Time of onset of the protocol qualifying organ dysfunction/failure will be recorded. For cardiovascular dysfunction, the time of organ dysfunction/failure is defined as the time of initiation of vasopressors. The time of pulmonary dysfunction/failure is defined as the time that the patient meets the appropriate $\text{PaO}_2/\text{FiO}_2$ (or $\text{SpO}_2/\text{FiO}_2$ ratio) ratio while on mechanical ventilation (for organ dysfunction/failure definitions, see [Table 2](#)). An arterial blood gas or recording of the patient's SpO_2 value within 2 hours of intubation will be required otherwise the 24 hour clock will begin at the time of intubation. Patients who have been on mechanical ventilation for more than 48 hours prior to the CCC call cannot use pulmonary dysfunction as the qualifying organ failure. These patients can be enrolled if they meet criteria for cardiovascular dysfunction.

Table 2 Organ dysfunction/failure definitions

System / organ	Definition
Cardiovascular System	
Hypotension, as defined as a systolic blood pressure <90 mmHg, or a mean arterial blood pressure ≤ 65 mmHg requiring vasopressors despite a) a volume infusion of 20 mL/kg crystalloid or colloid equivalent over 4-6 hours before randomisation or b) 30mL/kg crystalloid or colloid equivalent in the 24 hours prior to randomisation after consultation with the CCC.
 
NOTE 1: If hypotension and vasopressor requirement is in the setting of intubation, the patient must still be vasopressor-dependent 1 hour after intubation. Patients requiring vasopressors prior to intubation are eligible for the study.
 
NOTE 2: 10 mL/kg of colloids = 20 mL/kg crystalloids.

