7.6.10 Shock-free days

The number of shock-free days will be recorded up to Day 15. Shock-free is defined as a score <2 taken from the cardiovascular component of the modified SOFA score (see Appendix G).

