12.2.4 Calculation and derivation of Glasgow Coma Score

The calculation of the Glasgow Coma Score will be done electronically; investigators will only need to answer the individual questions in the eCRF.

For each of the categories of eye, verbal and motor response, a point score is assigned to the level of response. The Glasgow Coma Score is the sum of these three scores. For further details, see [Appendix F](#).

12.2.5 Calculation and derivation of the modified Sequential Organ Failure Assessment (SOFA) Scores

A point score is given to each of the variables recorded for the 5 categories of respiration, coagulation, liver, cardiovascular, and renal. The total modified SOFA score is calculated from the sum of these individual scores. A modified SOFA score will be calculated (five categories: respiration, coagulation, liver, cardiovascular, and renal) for all timepoints in [Table 1](#). The calculation of the modified SOFA score will be done electronically; investigators will only need to enter the values of the parameters measured into the eCRF.

The worst BP and saturation values of the day should be used, and if a drug holiday or no value is collected, the last assessment performed should be the value for that day.

For further details of the modified SOFA Score, see [Appendix G](#).

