1. MODIFIED SEQUENTIAL ORGAN FAILURE ASSESSMENT (SOFA) SCORE

	Modified SOFA Score				
	0	1	2	3	4
Respiration					
PaO ₂ /FiO ₂ (torr) ^a	>400	≤400	≤300	≤200 With respiratory support	≤100 With respiratory support
SpO ₂ /FiO ₂ (torr) ^{a, b}	≥512	<512	<357	<214 With respiratory support	<89 With respiratory support
Coagulation					
Platelets (x10 ³ /mm ³)	>150	≤150	≤100	≤50	≤20
Liver					
Bilirubin (mg/dL)	<1.2	1.2-1.9	2.0-5.9	6.0-11.9	>12.0
(μmol/L)	<20	20-32	33-101	102-204	>204
Cardiovascular					
Hypotension ^a	No hypotension	MAP <70 mm Hg	Dopamine ≤5 or dobutamine (any dose) ^b	Dopamine >5 or epi ≤0.1 or norepi ≤0.1 or phenylephrine ≤300 ^c or vasopressin <0.04 units/min	Dopamine >15 or epi >0.1 or norepi >0.1 or phenylephrine >300 ^c or vasopressin ≥0.04 units/min
Renal					
Creatinine (mg/dL)	<1.2	1.2-1.9	2.0-3.4	3.5-4.9	>5.0
(μmol/L)	<110	110-170	171-299	300-440	>440
or urine output				or <500 mL/day	or <200 mL/day

PaO₂: partial pressure of arterial oxygen; FiO₂: fraction of inspired oxygen; SpO₂: oxygen saturation by pulse oximetry; epi: epinephrine; norepi: norepinephrine; MAP: mean arterial pressure.

Clinical Study Protocol: Appendix G
Drug Substance AZD9773
Study Code D0620C00003
Appendix Edition Number 2

- 
- a The worst blood pressure and saturation values of the day should be used, and if no value is collected, the last assessment performed should be the value for that day or the last available (if within 48 hours). On days when laboratory results are unavailable, values will be extrapolated from the previous available values.
 - b Data on file.
 - c Adrenergic agents administered for at least 1 hour (doses given are in $\mu\text{g}/\text{kg}/\text{min}$).
To convert torr to kPa, multiply the value by 0.1333.

Vincent et al 1998

Vincent JL, de Mendonca A, Cantraine F, Moreno R, Takala J, Suter PM, et al. Use of the SOFA score to assess the incidence of organ dysfunction/failure in intensive care units: results of a multicenter, prospective study. Working group on “sepsis-related problems” of the European Society of Intensive Care Medicine. Crit Care Med 1998;26(11):1793-800.

Clinical Study Protocol Appendix H

Drug Substance	AZD9773
Study Code	D0620C00003
Edition Number	2
Date	██████████

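### Entry accepts any vasopressor but the cardiovascular SOFA component scores only six named agents, so a day supported solely by another one counts as shock-free

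*Protocol*

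**What the plan says.** **Entry.** Table 2 in Section 5.1 defines the cardiovascular criterion as low pressure "requiring vasopressors despite a) a volume infusion of 20 mL/kg crystalloid or colloid equivalent", with an alternative fluid volume that needs consultation with the co-ordinating centre. No vasopressor is named. Onset is dated the same way: "the time of organ dysfunction/failure is defined as the time of initiation of vasopressors".

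**Outcome score.** Section 7.6.3 states that "The SOFA score for the cardiovascular component does not account for the use of phenylephrine or vasopressin as vasopressor medications" and then assigns 3 or 4 to those two drugs by dose. Appendix G gives the whole component. Score 0 is no hypotension and score 1 is a mean arterial pressure below 70 mmHg. Score 2 is lower-dose dopamine "or dobutamine (any dose)". Scores 3 and 4 cover dopamine, epinephrine, norepinephrine, phenylephrine and vasopressin by dose, for example "or vasopressin <0.04 units/min" for score 3. There is no entry for any other agent.

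**Endpoints.** Section 7.6.10: "Shock-free is defined as a score <2 taken from the cardiovascular component of the modified SOFA score". Section 12.2.7: "Organ failure-free days will be designated for those days when the organ system modified SOFA score is" 1 or less. Section 12.2.5: "The calculation of the modified SOFA score will be done electronically" from the values that investigators enter.

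**The concern.** A patient can enter the trial in shock on a vasopressor that the outcome score does not recognise, stay on it, and be recorded as shock-free from the first scored day. Section 7.6.3 shows that the sponsor saw this kind of gap and closed it for two drugs. Every other agent was left as it was.

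Shock-free days and organ failure-free days are among the endpoints listed for formal analysis in Section 13.1, and Section 2.3 counts shock-free days and organ failure assessments among the important secondary endpoints. The trial is international, with about 100 centres (Section 4.1), so identical vasopressor practice everywhere cannot be taken for granted. Where an unlisted agent is used alone, the endpoint records drug choice and not shock.

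**Working it through.** The protocol gives no numerical figure for this point. Its only sample-size figure is for ventilator-free days (Section 13.4: SD 11.380, difference 4.2, 10% one-sided, 90% power). It reproduces: n per group = 2 × (1.2816 + 1.2816)² × 11.380² / 4.2² = 96.5, so 97, and power at 100 per group is 0.908. Nothing below depends on it.

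**Step 1. Apply Appendix G as written.** The component is 0 at a mean arterial pressure of 70 mmHg or above and 1 below 70, unless a listed agent raises it. Test pressures are 60 and 75 mmHg. Epinephrine and norepinephrine share the same cut-offs.

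| Support on the day | Score at 60 | Score at 75 | Shock-free (<2)? | Cardiovascular failure-free (1 or less)? |
|---|---|---|---|---|
| Dopamine 5 µg/kg/min | 2 | 2 | no | no |
| Dopamine 6 µg/kg/min | 3 | 3 | no | no |
| Dobutamine, any dose | 2 | 2 | no | no |
| Epinephrine 0.05 µg/kg/min | 3 | 3 | no | no |
| Norepinephrine 0.2 µg/kg/min | 4 | 4 | no | no |
| Phenylephrine, low dose | 3 | 3 | no | no |
| Vasopressin 0.03 units/min | 3 | 3 | no | no |
| Vasopressin 0.04 units/min | 4 | 4 | no | no |
| Any other vasopressor alone | 1 | 0 | **yes** | **yes** |
| No vasopressor | 1 | 0 | yes | yes |

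Every listed agent scores 2 to 4. An unlisted agent scores exactly as no vasopressor does.

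**Step 2. Compare with entry.** Under Table 2 the same support, with hypotension and the fluid requirement met, is cardiovascular failure. The two definitions therefore disagree about the same treatment.

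**Step 3. Illustrative size.** Let f be the share of an arm supported only by an unlisted agent, and d the number of such days within the 14-day window. The overstatement of that arm's mean shock-free days is f × d. Neither input is in the protocol; both are assumptions.

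| f | d = 2 | d = 5 | d = 14 |
|---|---|---|---|
| 1% | 0.02 | 0.05 | 0.14 |
| 5% | 0.10 | 0.25 | 0.70 |
| 10% | 0.20 | 0.50 | 1.40 |
| 20% | 0.40 | 1.00 | 2.80 |

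At f = 0 the effect is zero.

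**The case against.** **No affected patient is shown.** The protocol names no vasopressor outside the list, and the pressors given as examples in Appendix D are all on it. This stands: the gap is in the rule, and how often it bites is unknown.

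**The protocol means vasopressor status to inform the score.** Section 7.6.3 records vasopressor use daily, and Section 13.3.5 encourages investigators to use on/off vasopressor information to complete the cardiovascular component. This stands only in part. Section 13.3.5 deals with missing data and attaches no score to being on an unlisted agent. A day with a recorded pressure is not missing, and the score is computed electronically.

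**It is detail for the SAP.** A residual coding rule could sit there. But the protocol itself fixes the scoring table, the two added drugs and both cut-offs, and a derivation that follows them produces the misclassification.

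**Stronger readings that the documents do not support:**
- *Such a patient is free of organ failure.* Only the cardiovascular component is affected; other organs can still score above 1.
- *The treatment difference shrinks by the share of patients affected.* That requires all of those patients' shock days to be misclassified. A patient who also receives a listed agent scores 2 or more on that day.
- *One arm is favoured.* Allocation is central and blinded (Sections 6.2.1 and 6.3.1), so drug choice should be similar across arms.
- *Regional differences go unadjusted.* Region is a covariate in the model used for these endpoints (Sections 13.3.4 and 13.3.6). It adjusts for average regional differences but does not restore a treatment difference lost through misclassified days.

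**Conclusion.** The point holds as an inconsistency between the entry definition and the outcome score. Applied literally, a day supported only by a vasopressor outside the six named agents counts as shock-free and as free of cardiovascular failure.

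Its size cannot be established from the protocol. The grid above runs from 0.02 to 2.8 days on an arm mean, wholly on assumed inputs; the upper corner needs 20% of an arm on such an agent alone for all 14 days. The effect is nil if no such agent is used alone. Because the scored population includes patients who entered on pulmonary dysfunction only, a given share among patients with shock is a smaller share of the arm.

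The expected consequence, assuming that blinding keeps drug choice similar across arms, is mainly dilution of differences in shock-free and cardiovascular failure-free days. The modified SOFA summaries are also understated on those days. The primary endpoint and the sample size are unaffected. A reader might infer a directional bias or a threat to the main result; the documents support neither.

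**What to change.** Reconcile the outcome score with the entry definition. In Section 7.6.3 and Appendix G, state that any vasopressor outside the list places the cardiovascular component at 2 or more. The sponsor should set the exact grade. It does not matter for shock-free or failure-free days, because both cut-offs fall between 1 and 2; it affects only the SOFA summaries.

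Use one duration convention for the score and for the shock-free definition in Section 7.6.10. Appendix G already carries a minimum of 1 hour for adrenergic agents. If the score required 1 hour while shock-free status was lost with any use that day, a brief infusion would score below 2 and still not be shock-free.

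**Cost.** One scoring line and its programming. For a calendar-day convention, the data exist: Section 6.5.2 records the name, start date and stop date of concomitant drugs to Day 29. It requires vasopressor times and doses only around the loading dose, so keeping a 1-hour criterion needs an other-vasopressor tick on the SOFA eCRF page. The small downside is that unlisted agents are not graded by dose. No patient's treatment changes.
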